## Background

Despite the decline in fatal TBI incidence in recent years, TBI morbidity remains a public health challenge and is the leading cause of disability in the United States. Residual impairments have been estimated to occur in 67% to 100% of TBI survivors, with cognitive impairments being the most disabling sequelae. In addition, TBI has emerged as one of the most significant health risks to military personnel related to the wars in Iraq and Afghanistan and an important medical concern due to potential long-term physical, cognitive and functional disabilities. To combat these effects, new research is needed to identify mechanisms of injury that will lead to potential targets for therapeutic interventions that improve neurological outcome.

One promising area of research is the cerebral metabolic dysfunction following TBI. Studies of post-traumatic cerebral metabolism have shown that CMRGlc decreases for a period of days, weeks or months after injury with the duration and degree of hypometabolism correlating to level of consciousness and a strong predictor of long-term neurological outcome. However, specific changes in intermediary carbohydrate metabolic pathways have not yet been identified. In addition, the role of astrocyte metabolism in the post-injury metabolism has not been studied. This study uses *in vivo* C MRS at 3T, a novel method in the clinical study of TBI, to non-invasively study the metabolic fate and flux of glucose (metabolized in both neurons and astrocytes) and acetate (metabolized in astrocytes) through metabolic pathways during the hypometabolic period. In addition, we will study the association of decreased cerebral perfusion with changes in glucose and acetate metabolism following TBI, as changes in cerebral perfusion could profoundly affect cerebral metabolism by limiting substrate availability.

### Cellular Mechanisms Affecting Cerebral Metabolism

While, mitochondrial dysfunction has been proposed as a key factor contributing to the hypometabolic response following injury, the down regulation and/or inhibition of enzymes or cofactors associated with intermediary metabolism may also decrease glucose metabolism following TBI. For example, increased production of reactive oxygen species (ROS) such as superoxide radical, hydrogen peroxide, and hydroxyl radical following TBI could inactivate pyruvate dehydrogenase (PDH), due to its sensitivity to ROS. Impaired PDH activity after TBI would limit the flux of substrates into the TCA cycle, decreasing oxidative metabolism and increasing the flux of substrate through anaplerotic pathways as a way of supplying needed TCA cycle intermediates to affected cells.

### Astrocyte Metabolism and Intracellular Metabolic Compartmentation Following TBI

Still unclear is the role of metabolic coupling between astrocytes and neurons following TBI. It has long been recognized that astrocytes play a pivotal role in meeting the energy requirements of neurons through various metabolic pathways, including the glutamate-glutamine cycle which links the exchange of neurotransmitter glutamate (Glu) and glutamine (Gln) between glutamatergic neurons and astrocytes. Moreover, the net synthesis of Glu in neurons requires a flux of TCA cycle intermediates, notably Gln, from astrocytes as neurons lack the capacity to generate TCA cycle intermediates. The net synthesis of TCA cycle intermediates, Glu and Gln depends upon the entry of pyruvate via an anaplerotic pathway into the TCA cycle. In the brain this is exclusively achieved by pyruvate carboxylase (PC), an astrocyte specific enzyme. Numerous *in vitro* studies have shown that astrocytes supply TCA cycle substrates to neurons during periods of glucose and/or oxygen deprivation, suggesting that astrocytes may play an even greater nutritional role for neurons in the injured state. Given the essential role of neuron-astrocyte metabolic coupling in normal brain, a greater appreciation of the effect of TBI on metabolic coupling is an important and necessary contribution to understanding of metabolic dysfunction following TBI. Moreover, the identification of novel metabolic therapies that target astrocytes may prove important in limiting neurological injury. In

this study, we will use [1, 2  $^{13}\text{C}_2$ ] acetate as an astrocyte specific metabolic substrate together with [1- $^{13}\text{C}$ ] glucose to study injury-induced changes in neuron-astrocyte metabolic coupling.

### Decreased Cerebral Perfusion Following TBI

Decreased cerebral perfusion following TBI is associated with reductions in the utilization of glucose which could profoundly affect cerebral glucose metabolism by limiting substrate availability. In this study, we will use MR dynamic susceptibility contrast perfusion weighted imaging (DSC-PWI) to measure changes in cerebral perfusion in the hypometabolic period following TBI. DSC-PWI can provide a measure of tissue perfusion similar to results found using more traditional methods of CBF determination, with the advantage of relative higher spatial resolution, the absence of need for radioactive isotopes, and can be combined with other MRI studies in one evaluation.

### Tracking the Metabolic Fate of Glucose: $^{13}\text{C}$ -MR spectroscopy

In order to determine how glucose is being metabolized,  $^{13}\text{C}$  MRS offers an attractive, novel method to study alterations in multiple enzyme complexes following a TBI. The primary advantage of this technique arises from its ability to distinguish  $^{13}\text{C}$  incorporation into multiple metabolites as well as into the specific carbon positions within the same metabolite, resulting in a detailed analysis of the metabolic fate of  $^{13}\text{C}$  label . The relative  $^{13}\text{C}$  enrichment at each carbon position and the ratios between isotopomers of Glu and Gln gives additional information regarding enzyme usage and metabolic compartmentation . The acquisition of  $^{13}\text{C}$  spectra over time enables the dynamic measurement and calculation of in vivo rates of flux through metabolic pathways, an important technique to study in vivo cerebral metabolism. To our knowledge, the use of  $^{13}\text{C}$  glucose together with  $^{13}\text{C}$  acetate to measure metabolic flux simultaneously has not been performed in either the normal or injured human brain. In this study, we will use of [1- $^{13}\text{C}$ ] glucose together with [1, 2  $^{13}\text{C}_2$ ] acetate to measure changes in both neuronal and astrocyte metabolism in both TBI and control subjects.

### **Significance**

Detailed knowledge of the metabolic alterations following TBI will provide a significant advancement to our understanding of the hypometabolic response to TBI, which is key information for the future development and testing of novel therapeutic interventions that by-pass or compensate for the metabolic dysfunction.

### **Study Objectives**

The goals of this inter-departmental study are: 1) the clinical application of in vivo  $^{13}\text{C}$  MRS at 3T to identify specific metabolic alterations following TBI and 2) determine if changes in cerebral perfusion effect metabolism by limiting metabolic substrate flow into the brain following TBI.

### **Hypothesis**

We hypothesize that following TBI, metabolic pathways are altered causing an incomplete oxidative of glucose in neurons and astrocytes resulting in a decrease in cerebral metabolism.

### **Research Design and Methods**

#### Imaging Protocol Overview

All control and TBI subjects will undergo an identical MRS/MRI protocol and neurological exam. MRS/MRI will be performed on a 3T Siemens TIM Trio system equipped with a second radiofrequency channel (Siemens Medical Solutions, Erlangen, Germany) using a specially designed and manufactured  $^1\text{H}$ - $^{13}\text{C}$  dual tuned volume head coil (Advanced Imaging Research, Cleveland,

OH). Sagittal 3D T2 weighted (T2WI) and 3D T1 weighted (T1WI) MR images, reformatted in axial and coronal planes, will be obtained for image co-registration and segmentation. The 2D DSC-PWI sequence will be used to determine cerebral blood flow (CBF), cerebral blood volume (CBV), mean transit time (MTT), and the cerebral metabolic rate of oxygen (CMRO2). Detailed sequence description and image processing methods are explained below.

**TABLE 1. Imaging Parameters for 3.0T Siemens TIM Trio Scanner**

Pulse Sequence	Plane	TR (ms)	TE (ms)	Slice Thickness (mm)	FOV (mm  )	Time (min)	NA	Note
T2 SPC	3D sagittal	3200	458	1	290x232	4:30	1	matrix = 320x319x320, iPAT=2; ETL=139; BW=744Hz/px
T1 MP-RAGE	3D sagittal	1950	2.26	1	256x224	3:54	1	FA=90°, matrix = 256x256x246, BW=200Hz/px, iPAT=2
DSC-PWI	2D axial	1700	40	5 (20% gap)	220x220	1:30	1	Matrix=128x100, measures = 50, FA=90°, fat saturation, BW=1860Hz/px, Echo spacing =.72
ISIS-DEPT  C MRS	2D axial	2500			160x200	60:00	24	Waltz16  H decoupling, FA=45°, outer volume suppression, 200μs rectangular excitation pulse, voxel size = 7x5x6cm 

TOTAL IMAGING TIME: 70 minutes plus shimming time

### **In vivo C MRS**

#### [1-C] glucose and [1, 2-C2] acetate infusion protocol

To reduce the complicating effects of endogenous glucose or the conversion of acetate to glucose in the liver, both control and TBI subjects will undergo a hyperinsulemic euglycemic glucose clamp via insulin infusion (60mU · m^-2 · min) in conjunction with a variable infusion of 20% dextrose solution. Following the insulin clamp, 30 ml of 100% isotopically enriched [1-C] glucose and [1, 2-C2] acetate (Cambridge Isotope Laboratories, Andover, MA, USA) in a 20% w/v solution will be infused for 10 minutes followed by a constant infusion (3mg · kg · min) of 30% isotopically enriched [1-C] glucose and [1, 2-C2] acetate. This infusion protocol results in normoglycemic plasma glucose levels of ~ 5.3 mmol/L, which will be maintained for the duration of the C MRS experiment. Blood samples (0.5ml) will be drawn in duplicate at 5-minute intervals for the immediate measurement of plasma glucose level using an Accu-Chek glucose meter and for measuring plasma glucose and acetate isotopic enrichment by high-resolution H and C NMR spectroscopy.

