#### ISIS-DEPT C MRS sequence

Using the T2WI images, a 7 x 5 x 6 cm^3 volume covering portions of the fronto-parietal lobe will be positioned, avoiding areas of obvious contusion. Direct detection, localized in vivo C MRS spectra will be acquired using a gradient-spoiled semi-adiabatic distortionless enhanced polarization transfer (DEPT) sequence (TR = 2.5 sec, interpulse delay = 3.8 ms, 45° flip angle, 128 acquisitions and WALTZ-16 decoupling applied during the acquisition) with three-dimensional image selected in vivo spectroscopy (ISIS) localization and outer volume saturation. Spectra will be post-processed off-line using NUTS data processing software (Acorn NMR Inc., Livermore, CA). All relevant peaks will be identified and assigned by comparison to previously published values, integrated, and the relative amount of C incorporation into Glu and Gln will be calculated. To calculate the various flux

parameters, a two-compartment model of flow from [1-C] glucose and [1, 2-C2] acetate will be implemented in CWave software using modifications of previously published equations.

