#### **Plasma NMR spectroscopy**

The peripheral metabolism of infused C labeled substrates is a confounding factor when measuring metabolism in the brain. Acetate metabolism is known to occur in the liver, resulting in the synthesis of glucose by gluconeogenesis. In the brain, C labeled glucose produced in the liver would lead to isotopomer labeling patterns similar to the metabolism of [1, 2-C2] acetate resulting in a potential source of error in our experiments. As a result, the fractional C enrichment of all plasma glucose isotopomers will be calculated by C and H high resolution NMR using a Bruker 600 MHz spectrometer to correct brain isotopomer enrichment levels for the contribution of peripheral metabolism.

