#### **DSC-Perfusion Weighted imaging**

A 2D single shot gradient echo echo-planar imaging (EPI) sequence will be used to obtain DSC\_PWI using the following parameters: TR/TE = 1700/40 ms, FA = 90°, slice thickness = 5mm, matrix size = 128, and 50 measures. Gadolinium-DPTA (Gd-DTPA) contrast (0.1 mmol/kg) will be administered intravenously at the completion of the 5th scan. The resultant images are transferred to an offline program where CBV, CBF and MTT maps will be generated for each slice. To calculate CMRO2, an arterial input function is chosen from the M1 section of the middle cerebral artery for each subject. A least squares exponential fitting is used to minimize secondary circulation; a singular value decomposition deconvolution is then used to obtain estimates of CBF and CBV.

To determine the effect of substrate limitation on glucose metabolism the position of the MRS voxel will be overlaid on CBF, CBV, and CMRO2 maps using an automatic image overlay program developed in our laboratory incorporating routines from MATLAB (Version 7.0.4, MathWorks, Natick, MA, USA). The relative CBF (ml/100g/min), CBV (ml/100g), and CMRO2 (ml/100g/min) within the region of the MRS voxel will then be compared to the final C Glu and Gln enrichment pools to determine if substrate limitation correlates with metabolite enrichment.

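### Glucose-derived Glu and Gln enrichment is not scaled to each subject's plasma glucose enrichment, which varies with whole-body glucose disposal if unlabelled dextrose runs during labelling

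*Combined protocol and SAP*

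**What the plan says.** All places are in the combined protocol and SAP.

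- **Infusion protocol ([1-13C] glucose and [1, 2-13C2] acetate).** The clamp applies to everyone: "both control and TBI subjects will undergo a hyperinsulemic euglycemic glucose clamp via insulin infusion" at 60 mU/m²/min, "in conjunction with a variable infusion of 20% dextrose solution". The label comes next: "Following the insulin clamp, 30 ml of 100% isotopically enriched" glucose and acetate, "in a 20% w/v solution will be infused for 10 minutes followed by a constant infusion" at 3 mg/kg/min "of 30% isotopically enriched" substrate. Plasma glucose is to be held near 5.3 mmol/L throughout the MRS run. Blood is drawn every 5 minutes, partly to measure plasma glucose and acetate enrichment.
- **Plasma NMR spectroscopy.** The stated use of the plasma glucose isotopomers is "to correct brain isotopomer enrichment levels for the contribution of peripheral metabolism", explained as labelled glucose made by the liver from acetate.
- **ISIS-DEPT 13C MRS sequence.** The relative amount of 13C "incorporation into Glu and Gln will be calculated". A two-compartment flux model follows; its input function is not named.
- **DSC-Perfusion Weighted imaging.** CBF, CBV and CMRO2 in the voxel are compared with the final 13C "Glu and Gln enrichment pools to determine if substrate limitation correlates with metabolite enrichment".
- **Other adjustments.** The voxel tissue composition section corrects for grey and white matter. Statistical Analysis lists means with 95% confidence intervals, one-way ANOVA and Pearson correlations, with no covariate for plasma enrichment or dextrose rate.

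**The concern.** Brain Glu and Gln can only become as enriched in glucose-derived label as the plasma glucose feeding them. A fixed label infusion combined with a dextrose rate adjusted to each subject gives each subject a different plasma enrichment, set by whole-body glucose disposal and not by the brain. Removing liver-made label is a different correction and leaves this dilution in place.

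Two analyses are exposed. The perfusion comparison, which serves the second study objective, gains variance unrelated to perfusion, so a real correlation is weakened. The comparison of 10 TBI patients with 5 controls loses power, and is also biased if the groups need different amounts of dextrose on average.

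**Working it through.** The plan gives no plasma enrichment, power or sample-size figure, so there is nothing to reproduce. The checks below show the size of the effect under stated assumptions.

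**Inputs from the plan.** Maintenance infusion 3 mg/kg/min at 30% enrichment; bolus 30 ml × 20% w/v = 6 g; glucose near 5.3 mmol/L; 60-minute MRS run; 10 TBI patients and 5 controls.

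**Assumptions, none in the plan.** Unlabelled dextrose continues at D mg/kg/min; endogenous glucose output is zero; the labelled infusion is treated as all glucose, because the glucose/acetate split is not stated.

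**1. Steady-state plasma enrichment.** E = 0.30 × 3/(3 + D) = 0.9/(3 + D).

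| D (mg/kg/min) | 0 | 1 | 2 | 4 | 6 |
|---|---|---|---|---|---|
| E | 30% | 22.5% | 18% | 12.9% | 10% |

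Two subjects with identical brains at D = 2 and D = 6 differ by 18/10 = 1.8-fold. If less of the infusion is glucose, every E falls. At the same total disposal (5 and 9 mg/kg/min) the ratio is still 9/5 = 1.8.

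**2. Is the spread present within the scan?** A one-pool time course (70 kg, bolus all glucose, pool 1.6 to 2.5 dl/kg) gives, 60 minutes after the bolus, 25 to 27% at total disposal M = 4, 18 to 19% at M = 6 and 10 to 11% at M = 10 mg/kg/min. It is.

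**3. Perfusion correlation.** If measured enrichment is brain metabolism × E, with E independent of both metabolism and perfusion, the observed correlation is r × c/√(c² + e² + c²e²). Here c is the metabolic CV (assumed 0.20) and e is the CV of E.

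- D uniform on 1 to 6: mean E = 0.9 × ln(9/4)/5 = 0.146; mean E² = 0.81 × (1/4 − 1/9)/5 = 0.0225; e = 0.237. Observed r = 0.60 × 0.20/0.3135 = 0.38.
- D uniform on 1 to 3: e = 0.117, observed r = 0.515.
- D uniform on 2 to 4: e = 0.097, observed r = 0.537.

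**4. Group comparison.** Simulated two-sample t-test, 10 v 5, 20,000 runs, CV of M 25%, brain CV 20%.

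| Mean M, TBI v control | True TBI/control | Unscaled | Divided by E |
|---|---|---|---|
| 6 v 6 | 0.70 | ratio 0.70, power 50% | ratio 0.70, power 87% |
| 5 v 7 | 1.00 | ratio 1.40, 37% false positives | ratio 1.00, 5% |
| 5 v 7 | 0.70 | ratio 0.98, decrease found in 4% | ratio 0.70, 87% |

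With equal mean disposal there is no bias, only lost power. The opposite difference, 7 v 5, would give a ratio of about 5/7 = 0.71 with no brain difference, so the direction of any bias is open.

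**5. How well simple division works.** The table above assumes steady state. The 100% bolus followed by 30% maintenance means plasma enrichment is not steady, and Glu lags it. In the one-pool course (D constant throughout, pool size fixed, Glu turnover 0.03 to 0.06 per minute, 70 minutes), identical brains at D = 2 and D = 6 have a raw ratio of 1.54 to 1.85. After division by time-averaged plasma enrichment the ratio is 1.06 to 1.14, or up to 1.21 if the bolus period is included in the average.

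**The case against.** The strongest reply is that the plan never says unlabelled dextrose runs during labelling. The label is given after the clamp, and the dextrose is not described as unlabelled. If it has stopped, D = 0 and step 1 gives 30% for everyone. This stands as a limit: the dilution is inferred. Continuation is the more coherent reading, because a fixed-rate infusion cannot alone hold about 5.3 mmol/L in subjects with different disposal, and the clamp's stated purpose (limiting endogenous glucose and acetate-to-glucose conversion) applies during labelling. Even with dextrose stopped, a flat 30 ml bolus for every body weight and any remaining endogenous glucose would leave plasma enrichment unequal.

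Three further replies stand in part.

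- **Acetate and ratios.** Dextrose dilutes the glucose label only. The acetate-derived, astrocyte signal is not affected by this route. The background also describes isotopomer ratios as read-outs, and ratios within the glucose-derived label largely cancel a common scale factor. What is meant by relative incorporation is not defined.
- **The flux model.** Plasma acetate enrichment is measured but has no stated use in the hepatic correction, so the plasma curves may well be meant as model inputs. Modelled flux would then be largely protected. The incorporation and final pools are still separate outputs, and it is the pools that are compared with perfusion.
- **Eligibility.** Both groups exclude diabetes and unstable serum glucose, and TBI patients must be haemodynamically stable. This may narrow a difference in dextrose need but does not remove it.

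**Conclusion.** The point holds as a conditional gap in the analysis. If unlabelled dextrose continues, glucose-derived Glu and Gln enrichment varies with whole-body glucose disposal, and the plan does not scale the incorporation or the final pools for it. Under the assumed spreads, a true correlation of 0.60 with perfusion would appear as anything from 0.38 to about 0.54. With equal mean disposal, power for a 30% reduction would be 50% instead of 87%. Dextrose rates, CVs and pool sizes are all assumptions.

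A reader might infer that the TBI-control contrast is biased, and that insulin resistance in the patients would mask the hypometabolism being sought. The documents do not support that: they give no dextrose needs for either group, and the bias vanishes if the means are equal and reverses if patients need more. Nor do they support the inference that all label, or the modelled flux, is compromised. The data needed are already to be collected, so what is missing is a defined analysis step.

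**What to change.** - In the infusion protocol, state whether the variable dextrose continues during the label infusion and whether it is unlabelled. This asks for the procedure to be described, not changed.
- In the ISIS-DEPT section, name the measured plasma glucose and acetate enrichment curves as the input functions of the two-compartment model, and define relative incorporation.
- In the ISIS-DEPT and DSC-perfusion sections, use for the group and perfusion comparisons either the modelled flux or Glu and Gln enrichment divided by the same subject's time-averaged plasma precursor enrichment: plasma glucose for glucose-derived label, plasma acetate for acetate-derived label. State the averaging window.
- Report plasma enrichment and dextrose rate by group.

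The cost is wording and some analysis time; no new samples are needed. Two downsides: plasma NMR measurement error enters the ratio, and the simple ratio leaves a residual artefact of roughly 6 to 14% (up to about 21% with the bolus averaged in) under the illustrative assumptions above. Modelled flux is therefore preferable where it can be fitted.

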#### ISIS-DEPT C MRS sequence

Using the T2WI images, a 7 x 5 x 6 cm^3 volume covering portions of the fronto-parietal lobe will be positioned, avoiding areas of obvious contusion. Direct detection, localized in vivo C MRS spectra will be acquired using a gradient-spoiled semi-adiabatic distortionless enhanced polarization transfer (DEPT) sequence (TR = 2.5 sec, interpulse delay = 3.8 ms, 45° flip angle, 128 acquisitions and WALTZ-16 decoupling applied during the acquisition) with three-dimensional image selected in vivo spectroscopy (ISIS) localization and outer volume saturation. Spectra will be post-processed off-line using NUTS data processing software (Acorn NMR Inc., Livermore, CA). All relevant peaks will be identified and assigned by comparison to previously published values, integrated, and the relative amount of C incorporation into Glu and Gln will be calculated. To calculate the various flux

parameters, a two-compartment model of flow from [1-C] glucose and [1, 2-C2] acetate will be implemented in CWave software using modifications of previously published equations.

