#### C MRS voxel tissue composition

In vivo MRS does not have the spatial resolution or the sensitivity to eliminate partial volume effects of different tissue types. Using an automatic MRS voxel segmentation program developed in our laboratory incorporating routines from MATLAB (Version 7.0.4, MathWorks, Natick, MA, USA) and SPM5 (The Wellcome Department of Imaging Neuroscience, Institute of Neurology, University College London, London, England), the relative gray matter and white matter tissue components will be calculated and applied as correction to factors to the C enrichment curves.

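### Does the mismatch between NA 24 in Table 1 and 128 acquisitions in the sequence text affect the 13C MRS results?

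*Combined protocol and SAP*

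**What the plan says.** The section on the ISIS-DEPT 13C MRS sequence gives "TR = 2.5 sec, interpulse delay = 3.8 ms, 45° flip angle" and then "128 acquisitions and WALTZ-16 decoupling applied during the acquisition". The ISIS-DEPT row of Table 1 gives TR 2500 ms and, further along, "160x200 60:00 24 Waltz16". Under the table's headings "Time (min) NA Note", this means a time of 60:00 and an NA of 24. NA is not defined anywhere. The TR, flip angle, voxel size and decoupling scheme agree between the two places, so both describe the same scan.

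The last line of Table 1 reads "TOTAL IMAGING TIME: 70 minutes plus shimming time". The background section on 13C spectroscopy says that collecting spectra over time "enables the dynamic measurement and calculation of in vivo rates of flux through metabolic pathways". The section on voxel tissue composition applies tissue corrections to the enrichment curves. No section says how many spectra are collected in the hour, or whether they are summed before the flux model is fitted.

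The Imaging Protocol Overview states that "All control and TBI subjects will undergo an identical MRS/MRI protocol and neurological exam".

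**The concern.** The flux rates come from a series of spectra, so the acquisitions per spectrum set both the spacing of the time points and the noise in each. If 24 and 128 are both acquisitions per spectrum, they imply different series: one spectrum a minute, or one every 5 min 20 s. Reading NA as the number of spectra does not help, because 24 spectra of 128 acquisitions would not fit in the hour. A reader cannot tell from the document which series is planned. If the choice altered the precision of the flux estimates noticeably, or differed between patients and controls, it would bear on the main comparison of 10 patients with 5 controls.

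**Working it through.** **Inputs.** TR 2.5 s (sequence section and Table 1); 128 acquisitions (sequence section); NA 24 and 60:00 (Table 1); other row times 4:30, 3:54 and 1:30 (Table 1).

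**1. The table's own total.** 4:30 + 3:54 + 1:30 + 60:00 = 69:54, which agrees with the stated 70 minutes. The 60:00 is therefore not the slip.

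**2. Repetitions in the slot.** 3600 s / 2.5 s = 1440.

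**3. Each count as acquisitions per spectrum.**

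| Count | Time per spectrum | Whole spectra in 60:00 | Time used | Acquisitions in session |
|---|---|---|---|---|
| 24 | 24 × 2.5 s = 1:00 | 1440 / 24 = 60 | 60:00 | 1440 |
| 128 | 128 × 2.5 s = 5:20 | 1440 / 128 = 11.25, so 11 | 11 × 5:20 = 58:40 | 11 × 128 = 1408 |

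The slot excludes neither count. The conflict is between 24 and 128, not between either of them and the scan time.

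**4. Can both numbers be true together?**
- 24 spectra of 128: 24 × 128 × 2.5 s = 7680 s = 128 min, more than twice the slot.
- 24 equal spectra in the slot: 1440 / 24 = 60 acquisitions each, not 128.
- 24 cycles making up 128 shots: 128 / 24 = 5.33, not a whole number.

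The numbers do not reconcile on any plain reading. Mixed blocks or overlapping windows can be made to fit, but nothing in the document suggests them.

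**5. Signal over the session.** With independent noise, signal-to-noise grows with the square root of the acquisitions: √(1440 / 1408) = 1.011. The two counts differ by about 1%.

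**6. Signal per spectrum.** √(128 / 24) = 2.31. Summing short spectra recovers most of this: five of 24 make 120 acquisitions, and √(128 / 120) = 1.03.

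**7. Precision of a fitted rate.** The document gives no time constants, so this step rests on assumptions: a curve y(t) = A(1 − exp(−t/τ)), each spectrum observed as a block mean, noise variance proportional to 1/acquisitions, A and τ both estimated, and τ from 5 to 120 min. Standard errors of τ come from the inverse information matrix and are shown relative to 60 spectra of 24.

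| τ (min) | 11 × 128 (last 80 s unused) | 12 × 120 (full hour) |
|---|---|---|
| 5 | 1.036 | 1.030 |
| 10 | 1.026 | 1.013 |
| 20 | 1.036 | 1.007 |
| 30 | 1.044 | 1.007 |
| 60 | 1.056 | 1.008 |
| 120 | 1.062 | 1.008 |

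Twelve spectra of 120 are almost as coarse as 11 of 128 but use the whole hour. For τ of 20 min or more, the loss then falls below 1%. Most of the 4% to 6% in the middle column therefore comes from dropping the last 80 s, which the plan nowhere says it will do. Only at τ = 5 min does coarse sampling itself account for most of the loss, and there it is about 3%.

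**The case for a change.** The strongest case for acting is that the document gives one setting two values and no plain reading makes both true. It cannot be put down to the PDF conversion: the row is legible and 24 falls under NA. Table 1 also points away from NA meaning the number of spectra, since its perfusion row has NA 1 and lists its 50 repeats separately in the notes. All of this stands.

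Two further arguments carry less weight. The first is that the comparison with perfusion uses the final glutamate and glutamine enrichment. If that meant a single last spectrum, its noise would differ by the factor of 2.31 between the two counts. The document does not say that it means this, and summing the last few short spectra closes most of the gap, as step 6 shows. The second is that the plan contains two rival time grids. It contains none: the series of 60 and 11 points appear only if both numbers are taken as acquisitions per spectrum and the spectra are assumed to run back to back.

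**Conclusion.** The mismatch is real but clerical. Either count gives almost the same signal over the hour (ratio 1.011), and the same protocol applies to patients and controls, so the choice cannot bias the group comparison. In the simplified fit, the loss of precision from coarser sampling is 0.7% to 0.8% for time constants of 20 to 120 min, about 1% at 10 min and 3% at 5 min. The largest figure, with the last 80 s also discarded, is 6%.

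The Statistical Analysis section is mainly descriptive, and no sample size, error rate or eligibility rule depends on the count. Whoever runs the scanner must enter one value, and whoever processes the spectra will know it and can sum short spectra as needed. Settling which number was meant tidies the document but alters no result.

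This rests on three assumptions: noise averages independently, one count is used for all 15 subjects as the Imaging Protocol Overview promises, and the single-exponential curve is a fair guide to the two-compartment model that will actually be fitted. The documents do not show which count is intended, and the conclusion does not depend on it.
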